## 7.6 Pathology Correlation Procedures

Specifics of tissue handling:

Notification of a case pathologist (Drs. [name] or [name]) and Surgical Pathology Laboratory Grossing room at UHN by [name] of name, MRN and date of surgery of patient scheduled for oral/tongue resection.

2. Sample taken by GTx staff to Pathology on 2nd floor TGH. Accessioning of surgical specimen by technologist upon arrival from OR and verification of the specimen by case pathologist. Inform biobank personnel that the case may not be biobanked.
3. Fresh sample taken by GTx staff to small animal MRI on 7th floor Princess Margaret Discovery Tower (PMDT). T2-weighted (T2) and T1-weighted imaging of fresh sample within 2 hours of surgery.

4. Sample returned by GTx staff to Pathology on 2nd floor TGH. No incisions in the specimen are allowed to preserve the anatomy. Fixation and processing of the surgical specimen with neutral buffered formalin then overnight fixation of the specimen immersed in formalin. This may include injection of formalin into the specimen.
5. Gross description, including inspection orientation and measuring of the specimen and inking (with multiple colors to determine margin status and to aid in orientation) according to standard operating procedure. Recording of data on a requisition sheet.
6. Removal of stitches and/or sutures of specimen by Head and Neck pathologists/pathology fellow.
7. Gel embedding of sample, including MR visible markers to aid in identifying slice location. Once complete, fixed sample taken by GTx staff to small animal MRI on 7th floor PMDT for T2 and T1-weighted imaging.
8. Sample returned by GTx staff to Pathology on 2nd floor TGH. Sectioning at a 3mm interval will be done by a head and neck pathologist/fellow. Gross digital pictures of each section will be taken. Sections will then be sent for paraffin infiltration by UHN pathology.
9. Histologic wholmount processing (further sectioning to 4-6 $\mu$ m thickness, mounting of sections on slides, staining with hematoxylin and eosin (H&E) stain). Each paraffin bock and slide will contain a label that includes the accession number and a number for identification of a section.
10. Return of stained sections to UHN pathology. An e-mail of acknowledgement of receipt will be sent to [name] and [name] by the receiving pathologist. Slides will be taken by GTx staff to Advanced Optical Microscopy Facility on 15th floor PMDT and scanned at histologic resolution (20x) with an Aperio scanner.
11. Outlining of malignant and ablated areas of surgical section in marker to be completed by the head and neck pathologist. The marked histologic slides will then be digitized and reconstructed into whole mount sections. Slides with outlined tumours will be digitized using a flat-bed scanner at 300dpi.
12. All cancerous regions marked and contoured on pathology will be registered on the corresponding parametric maps from each MRI data set. The MRI data will be registered to the post-resection cone-beam CT scan and the original planning CT image. This will register the pathological contours with those contoured by the radiation oncologists in step 7.2.9.

## 7.7 Metrics

- 7.7.1 Analysis will correlate the pathological sampling to the imaging. Specifically, we will compare the number of samples that show superficial disease and how this matches the location of the GTV as determined by CT imaging alone (GTV-std)

and the location of the GTV as determined by the combination of CT imaging and navigated endoscopy (GTV-endo).

- 7.7.2 Analysis will correlate the pathological sampling to the imaging. Specifically, we will measure the overlap of the pathology with the tumour defined using CT imaging alone, and the overlap of the pathology with the mapping of the superficial extent of the disease determined during surgery using either the pointing tool or navigated endoscopy.
- 7.7.3 Concordance of GTV-std and GTV-endo using conformity indices such as DICE, or STAPLE. These metrics estimate the differences between the GTV contours.

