## 2 BACKGROUND AND RATIONALE

### 2.1 Head and Neck Radiotherapy

Approximately half of cancer patients require radiation therapy (RT)\* at some point during their care. Technological advances in RT, such as intensity modulation (IMRT) and image guidance (IGRT), allow radiation dose delivery with high accuracy and millimeter precision. RT planning can be thought of as a serial, step wise chain-like process where each link depends on the previous one. As these technical links are improved and strengthened, accurate definition of the target is now emerging as the weakest step in the RT process. Accurate target definition is fundamental to all subsequent treatment planning and delivery and is critical for successful RT. Incorrect target definition can result in poorer outcomes through either undercontouring (less tumour control), overcontouring (more normal tissue toxicity), and/or both. For head and neck (H&N) cancer, the role of various combinations of radiological imaging in target delineation has been investigated with respect to target delineation at depth. However, contouring with only standard radiological methods often misses superficial disease when compared to pathological sampling.

For head and neck cancers, endoscopy is invaluable in visualizing the superficial, radiographically occult extent of disease. Relation of these findings to the planning environment, however, is based primarily on the treating clinician's recall of the endoscopically visible disease relative to anatomical landmarks, a process subject to substantial contouring bias, error, and uncertainty in delineating the target or gross tumour volume (GTV).

Endoscopic examination of involved endothelial surfaces plays a critical albeit qualitative role in target delineation revealing superficial visible tumour extending beyond the invading disease apparent on volumetric imaging studies. In current practice, the clinician integrates the endoscopic findings into the treatment plan using their clinical judgment, recollection of anatomical landmarks and experience to define a target volume. Although clinical practice may vary, permanent records of the endoscopic procedure such as screen captures are not typically stored in the medical record. The subjectivity of this practice is evident in the large inter-observer variations observed in most contouring studies that include the physical exam.

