### 2.2 Spatially Registered Endoscopy

To address these issues and improve contouring of superficial disease, we have designed and prototyped a novel platform that uses endoscopic tracking and image analysis tools for the accurate registration of endoscopic images to the treatment planning CT. Disease visible on endoscopy can then be contoured and registered to the planning CT, allowing inclusion of superficial disease invisible on the volumetric CT image dataset into the treatment plan.

Specifically, contouring can be performed on 2D endoscopic images, projected into 3D image space and imported into the treatment planning software. Our "optical simulation" (or endoscopic contouring) technology employs 3 fundamental technologies: an optical imaging

system, tracking technology, and image registration software. These technologies have been integrated into a single platform developed primarily for image-guided surgery which has been used in other REB-approved trials. The optical systems used in our initial studies were flexible endoscopes typically used in patient physical exams. Both real and virtual endoscopic images can be simultaneously displayed or, using various transparent display techniques can be overlaid on each other. Orthogonal views are also displayed showing the camera coordinates and contours.

The endoscopic contouring was demonstrated in pilot clinical studies with accuracies of ~3 mm on patients each with early stage (T1) glottic cancer. Endoscopic imaging was performed shortly after acquisition of the planning CT images. Patients were examined in the same position as the CT imaging, including fixation mask. Video and tracking information was recorded, allowing retrospective analysis. The 15 minute procedure was well tolerated by all subjects. Clinicians reviewed the video for frames displaying the tumour. Concordance between the endoscopic contours and those generated by the CT images alone were excellent along the superficial extent of the disease.

These cases were selected deliberately to be visible on both the optical and CT imaging, providing confirmation of contour concordance and as proof of concept. In contrast to this protocol, no suspicious submucosal extension was allowed in these patients. The study concluded optical simulation was feasible in these patients.

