### **4 Study Design**

#### **4.1 Overview**

- 4.1.1 This is a single centre, single arm feasibility study comparing target delineation of GTV for H&N cancer to pathology using either standard CT-based contouring or spatially registered endoscopy combined with CT-based contouring.
- 4.1.2 Oral cancer surgery will be performed under image-guidance, including a standard contrast-enhanced CT scan immediately prior to the resection procedure. This CT scan will replicate the standard radiation planning CT scan and will be used for delineation of the GTV-std. External fiducial markers will be placed on the patient for registration of the navigation tools to the CT image coordinate system.
- 4.1.3 During surgery, the superficial lesion will be mapped using either a standard pointing tool that will be used by the surgeon to outline the lesion or navigated endoscopy will be performed of the superficial disease visible in the oral cavity. The endoscopic video will be spatially registered to the prior CT scan and used post-procedure for endoscopic contouring as an aid in delineation of the GTV.
- 4.1.4 The tissue will be marked along all planned excisions and resected using standard protocols. The surgical specimen will be mounted and scanned fresh in the OR using the CT scanner and a small animal MRI for correlative pathology. The sample will be prepared for whole mount pathology mapping by embedding the fixed tissue in a gel. The sample will be imaged again using the small animal MRI. It will then be delivered to pathology whole-mount section and identification of disease margins, both superficial and at depth. Details of the pathology workflow are in Section 7.6.
- 4.1.5 Following the procedure, contouring of the GTV will be performed by a radiation oncologist unfamiliar with the surgery and using only the CT image. The mapping

of the superficial lesion (from 4.1.3) will be added to the CT image and the errors between the standard CT-based contouring and the extent of the superficial lesion will be measured. The standard contours and lesion mapping will be compared to pathology for concordance and volume.

[figure not shown]

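### Section 7.7.1 scores GTV-std and GTV-endo only on disease-positive samples, so it tends to favour the larger contour, and no metric in 7.7 counts disease-free tissue inside GTV-endo

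*Protocol*

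**What the plan says.** Section 7.7 (Metrics) lists three analyses.

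- **7.7.1** sets both contours against pathology: "we will compare the number of samples that show superficial disease and how this matches the location of the GTV", first for GTV-std (CT alone) and then for "the location of the GTV as determined by the combination of CT imaging and navigated endoscopy (GTV-endo").
- **7.7.2** measures how far pathology overlaps the CT-defined tumour. Its second comparison, cut here before its final word, is: "the overlap of the pathology with the mapping of the superficial extent of the disease determined during surgery using either the pointing tool or navigated". This second comparison uses the map, not GTV-endo, and no overlap index is named.
- **7.7.3** applies conformity indices such as Dice or STAPLE to GTV-std and GTV-endo, compared with each other and not with pathology.

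Section 4.1.5 adds: "The standard contours and lesion mapping will be compared to pathology for concordance and volume". This again concerns the CT contours and the map.

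On how endoscopy enters the contour, section 4.1.3 says that the registered video is "used post-procedure for endoscopic contouring as an aid in delineation of the GTV". Section 4.1.5 says that the mapping "of the superficial lesion (from 4.1.3) will be added to the CT image". Section 2.2 gives the aim as "allowing inclusion of superficial disease invisible on the volumetric CT image dataset into the treatment plan".

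Section 2.1 names two harms of wrong target definition: undercontouring, with less tumour control, and "overcontouring (more normal tissue toxicity").

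**The concern.** The study asks whether endoscopic contouring is needed, judged by pathology. Within 7.7, only 7.7.1 puts GTV-endo itself against pathology, and the unit it counts is the sample that shows disease. That answers how much of the disease lies inside the contour. It does not answer how much of the contour is free of disease.

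On such a measure, enlarging a contour can keep or raise the score but never lower it. An endoscopic contour that spreads onto normal mucosa would look as good as an accurate one, or better than a tight CT contour, and 7.7.1 would not show the overcontouring that the protocol's own rationale treats as harmful.

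**Working it through.** The protocol gives no figure to reproduce here: no effect size, test or success threshold. The check is therefore set logic plus an illustration on assumed geometry.

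**1. Measures.** Let P be the pathology-positive superficial region and G a contour.

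- Coverage = |P∩G| / |P|. This is the reading of 7.7.1.
- Positive predictive value (PPV) = |P∩G| / |G|. The pathology-negative fraction is 1 − PPV.
- Dice = 2|P∩G| / (|P| + |G|).

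**2. If GTV-endo contains GTV-std (union).** P∩GTV-std lies inside P∩GTV-endo, so coverage of GTV-endo is at least that of GTV-std, always. If CT covers a share c of the positives and the map captures a share g of the rest, coverage is c + (1 − c)g. With assumed c = 0.70, g = 0.40 gives 0.70 + 0.30 × 0.40 = 0.82, and g = 0.20 gives 0.76. These inputs only show the direction.

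**3. Overcontouring that coverage does not see.** Assume disease of 15 mm radius, an exact GTV-std, and a GTV-endo of 22 mm radius on the same centre.

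- Coverage: 1.00 for both.
- PPV: 1.00 against 15²/22² = 225/484 = 0.46.
- Dice: 1.00 against 2 × 225/(225 + 484) = 450/709 = 0.63.

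**4. Coverage and Dice can disagree on which contour is better.** Assume the same disease, a 15 mm GTV-std displaced 2 mm one way, an 18 mm map displaced 3 mm the other way, and GTV-endo as their union. Coverage rises from 0.92 to 1.00, while PPV falls from 0.92 to 0.67 and Dice from 0.92 to 0.80.

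**5. If GTV-endo is re-delineated rather than added.** Assume a GTV-std of 17 mm radius centred on the disease, and a GTV-endo that follows a 14 mm map displaced 3 mm. Coverage is 1.00 for GTV-std and 0.81 for GTV-endo, so GTV-endo can score worse.

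**6. Random geometry, 3000 draws.** Disease radius 15 mm; GTV-std radius 10–19 mm with centre SD 2 mm per axis; map radius 12–18 mm with centre SD 3/√2 mm per axis. The last figure is scaled to the accuracy of about 3 mm in section 2.2; the others are assumed.

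| Comparison with GTV-std | Share of draws in which GTV-endo is worse |
|---|---|
| Union, coverage | 0% |
| Union, Dice against pathology | 34% |
| GTV-endo follows the map alone (extreme re-delineation), coverage | 45% |

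Only the 0% is general. The other two depend on the assumed geometry.

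**7. Do the other metrics fill the gap?** 7.7.2 and 4.1.5 can show an oversized map, but neither reports on GTV-endo. 7.7.3 is symmetric in the two contours. In step 3 the Dice between GTV-std and GTV-endo is 0.63; had the disease been 22 mm, with endoscopy exact and CT too small, it would also be 0.63. It shows that the contours differ, not which is nearer to pathology.

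**The case against.** A reader might infer that GTV-endo can never score worse and that the comparison favours endoscopy by construction. The documents do not support that. No section defines GTV-endo as GTV-std plus the map. Section 4.1.3 describes endoscopy as an aid to delineation, which lets a contour shrink or shift, and 4.1.5 adds the map to the CT image, not to the GTV-std contour. The workflow in 7.2.8 and 7.2.9 (contour on CT, then register the lesion) has no re-contouring step and the aim in 2.2 is inclusion, so an additive reading is plausible, but it remains an inference.

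A reader might also infer that overcontouring goes unmeasured in the whole study. That is too strong. Section 4.1.5 compares the CT contours and the map with pathology for concordance and volume, 7.7.2 measures overlap for each, and 4.2.6 measures overlap and differences between map and GTV. A map drawn too large could be seen there.

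It can further be said that 7.7.1 is loosely worded and fixes no denominator, that computational detail may sit in an analysis plan, and that a feasibility study of up to 10 patients with no test or threshold takes no formal decision on this metric. Counting positive samples outside the CT contour also directly serves the objective, in the protocol summary, of assessing disease beyond what CT shows. All of this lowers the stakes. It does not change the fact that 7.7.1 names disease-positive samples as what is counted, or that GTV-endo meets pathology nowhere else in 7.7.

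**Conclusion.** The point holds in conditional form. As worded, 7.7.1 is a one-sided coverage measure that tends to favour the larger contour. If GTV-endo is the union of GTV-std and the map, it cannot score below GTV-std; if it is re-delineated, it can. Under either construction, no item in 7.7 counts disease-free tissue inside GTV-endo.

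The size of any distortion cannot be derived from the protocol. The 70%, 40% and 20% shares and the disc geometries are assumptions that show direction only. What does not depend on them is that coverage is blind to disease-free tissue inside a contour. With a descriptive design of up to 10 patients, this is a worthwhile correction to the metric and not a reason to doubt the study as a whole.

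**What to change.** In 7.7.1:

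1. State how GTV-endo is formed: re-delineation with the map in view, or union of GTV-std and the map.
2. For each patient, and for both GTV-std and GTV-endo, report against the registered whole-mount pathology (a) the fraction of pathology-positive superficial area inside the contour, and (b) the fraction of contoured superficial area within the resected specimen that is pathology-negative. Dice against pathology could replace (b). The limit to the specimen is needed because tissue left in the patient has no pathology.
3. For the region in GTV-endo but outside GTV-std, report the proportion that contains disease.
4. Base the conclusion on coverage and overcontouring together.

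The cost is a wording change and one extra calculation. Section 7.6 (items 11 and 12) already has the cancerous regions outlined on the whole-mount sections and registered to the planning CT, and under 7.2.5 the marked excision includes an added margin, so specimens should contain disease-free tissue. No new patient procedure or data collection is needed.

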## 7.8 Data Collection

For each patient, a single anonymized identifier will be used. The following data will be collected:

- Date of surgery
- Tumour site
- Tumour type
- CT images (from 7.2.1)
- Intraoperative cone beam CT (from 7.3.1)
- Endoscopic video (from 7.5.1)
- Pathology data, including whole mount images (7.6) and tumour classification from pathology reports

A data collection summary sheet will be stored for each patient.

## 8 Safety

### 8.1 CT Scan

8.1.1 An additional contrast-enhanced CT scan will be required. The additional dose to the patient resulting from this scan is minor. The routine CT Head & Neck scan conducted as standard of care at UHN delivers ionizing radiation of 3.0-5.0 mSv to the patient. For comparison, this exposure is equivalent to about one year of background radiation exposure from living in North America (2.0 - 3.0 mSv), while for people living on the plateaus of Colorado or New Mexico, the annual background radiation exposure is 3.5 - 4.5 mSv. REB 11-0192-C was granted to image a very similar patient population to the present study, with similar demographics and the same diagnosis.

## 9 STATISTICAL CONSIDERATION

### 9.1 Sample Size

9.1.1 This study will accrue up to 10 patients with H&N cancer, leading to 10 whole mount pathology samples in total. The reporting of the pathology findings will be spatially correlated to the imaging. If possible, other pathological findings will be used in the analysis if sufficient spatial correlation can be recovered based on tissue markings used with the excision.

9.1.2 The number of H&N oral cancer cases that proceed to surgery is ~5 per week. Assuming an accrual of 10%, this would average approximately 1-2 cases per month.

## 10 SOURCE DOCUMENTS AND ACCESS TO SOURCE DATA/DOCUMENTS

Appropriate documentation will be maintained for this trial, in compliance with ICH E6, Section 4.9 and OCI/PMH institutional requirements for the protection of confidentiality of subjects. The documentation will be stored for a period of 25 years in accordance with Health Canada Regulations.

Only designated personnel will have access to records. Only authorized representatives of the sponsor or regulatory agencies will be allowed to examine (and when required by applicable law, to copy) clinical records for the purposes of quality assurance reviews, audits, or evaluation of the study safety and progress.

## **11 ETHICS/PROTECTION OF HUMAN SUBJECTS**

### **11.1 Ethical Standard**

The PI will ensure that this study is conducted in full conformity with the principles set forth in the Declaration of Helsinki, CIOMS, International Ethical Guidelines for Biomedical Research Involving Human Subjects (2002), The Belmont Report: Ethical Principles and Guidelines for the Protection of Human Subjects of Research of the US National Commission for the Protection of Human Subjects of Biomedical and Behavioral Research (April 18, 1979) and codified in 45 CFR Part 46 and/or the ICH E6; 62 Federal Regulations 25691 (1997).

### **11.2 Institutional Review Board**

The institution must provide for the review and approval of this protocol and the associated informed consent documents, and relevant recruitment material by an appropriate independent research ethics board [REB]. Any amendments to the protocol or informed consent materials must also be approved before they are placed into use.

### **11.3 Informed Consent Process**

Informed consent is a process that is initiated prior to the individual's agreeing to participate in the study and continuing throughout the individual's study participation. Extensive discussion of risks and possible benefits of this therapy will be provided to the subjects and their families. Consent forms, separate from the protocol document, describing in detail the study interventions/products, study procedures, and risks are given to the subject and written documentation of informed consent is required prior to starting intervention/administering study product (see Appendix for sample of Informed Consent Form). Consent forms will be REB-approved and the subject will be asked to read and review the document. Approved consent forms may be available translated into other languages, as applicable.

Upon reviewing the document, the investigator will explain the research study to the subject and answer any questions that may arise. The subjects will sign the informed consent document prior to any procedures being done specifically for the study. The subjects should have the opportunity to discuss the study with their surrogates or think about it prior to agreeing to participate. The subjects may withdraw consent at any time throughout the course of the trial. A copy of the informed consent document will be given to the subjects for their records. The privacy, rights and welfare of the subjects will be protected by emphasizing, to them, that the quality of their medical care will not be adversely affected if they decline to participate in this study.

